5. AMENDMENTS AND UPDATES

Amendmen t number	Date	Protocol section(s) changed	Summary of amendment(s)	Reason
1	31 August 2021	Sections 3, 4, 6, 7, 8, and 9	An amendment for Phase 3 includes a data refresh and updated analysis of Phases 1 and 2 with increased sample size and data through 31 August 2021. Responsible parties were updated.	Increased sample size and longer study period.

6. MILESTONES

Milestone	Planned date
Finalization of study protocol	February 2020
Submission to the Institutional Review Board (IRB)	February 2020
Start of structured data collection	December 2019
End of structured data collection	January 2020
Interim Report (analyses to meet the Phase 1 objectives)	May 2020
Start of chart review	May 2020
End of chart review	July 2020
Final Report (analyses to meet the Phase 2 objectives)	October 2020
Finalization of Phase 3 study protocol	September 2021
Phase 3 Submission to the Institutional Review Board (IRB)	September 2021
Structured data extraction for Phase 3	October 2021
Start of chart review for Phase 3	November 2021
End of chart review for Phase 3	January 2022
Analysis for Phase 3	February 2022
Final Report including updated analysis for Phase 3	March 2022

7. RATIONALE AND BACKGROUND

Lung cancer is the second most common cancer in the United States (US) with approximately 235,760 new lung cancer diagnoses estimated to occur in 2021 with 131,880 deaths during this time.[2] Worldwide, lung cancer is a predominant cause of cancer related mortality as the disease is usually diagnosed late. At the initial diagnosis, almost 70% of patients with lung cancer either have a locally advanced disease or have distant metastases. The median overall survival (OS) from diagnosis for patients with stage IV anaplastic lymphoma kinase (ALK)-positive non-small cell lung cancer (NSCLC) is 6.8 years. [3]

Lung cancer is of mainly 2 types, small cell lung cancer and non-small cell lung cancer (NSCLC). These 2 subtypes are treated differently through different chemotherapy and radiotherapy regimens. NSCLC comprises around 85-90% of all lung cancers with 40% of these having adenocarcinoma histology. This type of lung cancer occurs mainly in current or former smokers, but it is also the most common type of lung cancer seen in non-smokers. It is more common in women than in men, and it is more likely to occur in younger people than other types of lung cancer. [4]

A genetic alteration of the anaplastic lymphoma kinase (ALK) gene is present in 3-5% of NSCLCs. Over the last decade, there has been an increase in the number of oral anticancer agents available for use as treatment. The availability of orally available cancer treatments has made it possible for patients to receive their treatments without having to travel long distances. [5]

Biomarker driven therapies have revolutionized the treatment of non-small cell lung cancer (NSCLC). The first FDA-approved ALK inhibitor for ALK+ (ALK+) metastatic NSCLC treatment in 2011, crizotinib, has shown significant improvement in progression-free survival (PFS) and tumor responses in patients with metastatic NSCLC who carry the ALK gene rearrangement. While crizotinib has demonstrated significant improvement in PFS in Phase 3 studies, a subset of patients may develop acquired resistance to the drug after approximately 12 months, most likely due to secondary mutations to the ALK gene. [6-15]

For patients who progress on crizotinib, second generation ALK-inhibitors have been developed. Additional ALK-inhibitors that have subsequently been approved include ceritinib (April 2014), alectinib (December 2015), and brigatinib (April 2017).

Alectinib is a second-generation kinase inhibitor indicated for the treatment of patients with ALK+ metastatic NSCLC. Alectinib was first FDA approved in December 2015 for the treatment of ALK+ NSCLC in patients following treatment with the first generation ALK inhibitor crizotinib. In November of 2017, the FDA approved alectinib for use as first-line treatment for ALK+ metastatic NSCLC.

The approval was based on the Phase 3 ALEX trial of 303 first-line ALK+ NSCLC patients. Treatment with alectinib demonstrated a significantly reduced risk of progression or death by 47 percent (HR=0.53, 95 percent CI: 0.38, 0.73, p<0.0001) compared to crizotinib. Median

PFS was 25.7 months (95 percent CI: 19.9, not estimable) for patients treated with alectinib compared with 10.4 months (95 percent CI: 7.7, 14.6) for patients who received crizotinib. Treatment with alectinib also reduced the risk of the brain or central nervous system (CNS) metastasis compared to crizotinib by 84 percent (HR=0.16, 95 percent CI: 0.10, 0.28, p<0.0001).[1]

Likewise, ceritinib (Zykadia®), has been tested in the frontline setting. In the ASCEND-4 Phase 3 trial, ceritinib was compared to a platinum/pemetrexed demonstrating a median progression free survival of 16.6 months as compared to only 8.1 months in the platinum/pemetrexed chemotherapy arm. Other comparisons of second and third generation ALK inhibitors to ceritinib are ongoing.[16]

More recently, in November 2018, the FDA granted accelerated approval to lorlatinib for patients with ALK+ metastatic NSCLC whose disease has progressed on crizotinib and at least one other ALK inhibitor or whose disease has progressed on alectinib or ceritinib as the first ALK inhibitor therapy.[17] The accelerated FDA approval was converted to a full approval and the indication was expanded to include first-line treatment for patients with ALK+ metastatic NSCLC in March 2021. [18]

With the availability of several therapeutic agents, current treatment patterns and outcomes with use of multiple ALK-inhibitor treatments in sequence are not well understood. For patients with ALK positive NSCLC, first-line therapy with alectinib is the preferred treatment option, however, sequence of therapy is not well-defined. This study aims to understand patient profiles, treatment patterns, and clinical outcomes among ALK+ NSCLC patients treated with alectinib, and post-alectinib treatment patterns and outcomes.

8. RESEARCH QUESTION AND OBJECTIVES

The overall goal of this study is to understand the patient characteristics, treatment patterns, and clinical outcomes of ALK+ NSCLC patients treated with alectinib in US community oncology practices. To efficiently and effectively address research questions, we will leverage both the structured and unstructured data of the EHR and execute the study in 2 phases. Phase 1 will consider a population of ALK+ NSCLC patients who received alectinib during the study intake period. For Phase 2, a sample of patients who received alectinib as front-line therapy will be selected for chart review.

The study plan utilizes structured data and unstructured (chart review data). For the landscape objectives in Phase 1, study data will originate from structured fields of the EHR, which are controlled and mapped data elements, and will be available ahead of chart review data. For the second phase, specific study objectives will be assessed among a subset of patients selected for chart review using both structured and unstructured data. In this phase, data will also be derived from unstructured fields in the EHR, such as providers' free-text notes, which can only be captured through a chart review.

Phase 1: Landscape Objectives (structured data):

These analyses will be performed for all study-eligible patients who received alectinib (in any line of therapy) during the study identification period. Results will be presented overall as well as for the subgroups of patients who received a subsequent therapy following alectinib:

- 1. Describe the demographic and clinical characteristics of ALK+ NSCLC patients who received alectinib overall, and stratified by subsequent treatment following alectinib
- 2. Characterize post-alectinib treatment patterns and sequencing of other ALK inhibitors; categorizing type of treatments received after alectinib
- 3. Estimate duration of therapy with alectinib and duration of therapy for post-alectinib treatment
- 4. Examine overall survival of patients post-alectinib stratified by subsequent treatment following alectinib

Phase 2: Chart Review Objectives (unstructured data):

For Phase 2, structured data will be supplemented with a targeted chart review to confirm alectinib and other ALK inhibitor oral drug therapy information and collect additional unstructured data for a sample of front-line alectinib (i.e., first treatment administration of alectinib not preceded by any other product for NSCLC therapy) patients from the eligible study population. Results will be presented for all patients selected for chart review, as well as the subgroups of patients who received a subsequent therapy following alectinib:

- 5. Describe the demographic and clinical characteristics of ALK+ NSCLC patients who received alectinib overall, and stratified by subsequent treatment following alectinib
- 6. Characterize post-alectinib treatment patterns and sequencing of other ALK inhibitors; categorizing type of treatments received after alectinib
- 7. Estimate duration of therapy with alectinib and duration of therapy for post-alectinib treatment
- 8. Examine reasons for treatment discontinuation of alectinib and post-alectinib treatment
- 9. Estimate progression-free survival (PFS) of patients post-alectinib stratified by subsequent treatment (as supported by the final sample size)
- 10. Examine overall survival of patients post-alectinib stratified by subsequent treatment (as supported by the final sample size)

Phase 3: Data Refresh (structured and unstructured data) and Exploratory Analysis (structured data)

For Phase 3, the structured and unstructured data study objectives (Phase 1 and Phase 2) will be updated with additional follow-up time through 31 August 2021..

In addition, patients initiating lorlatinib following FDA approval to end of study period will be identified in structured data and the following exploratory objectives will be examined:

- 11. Identify patients initiating lorlatinib and monitor lorlatinib uptake over time
 - Evaluate demographic and clinical characteristics of patients receiving lorlatinib
 - Characterize lorlatinib treatment sequencing utilization and patterns

9. RESEARCH METHODS

[figure not shown]
9.1. Study design Phases 1 and 2

This is a retrospective, observational, descriptive study to examine patient characteristics, treatment patterns, and outcomes of patients ALK+ NSCLC treated in The US Oncology Network and Non-Network practices utilizing the iKM EHR. During phases 1 and 2, patients who have evidence of receiving alectinib during 01 June 2017 and 30 June 2019 will be eligible for inclusion in the study.

Complete study eligibility criteria and cohort definitions are presented in Section 9.3. Study-eligible patients will be followed longitudinally until 31 December 2019, last patient record or date of death, whichever occurs first.

An overview of the study design for Phases 1 and 2 is presented below.

Figure 1. Phases 1 and 2 study design

^{*}last visit = last physical encounter; X = Additional visit or record of death

Phase 1 objectives will be assessed among patients who meet study eligibility criteria as specified in Section 9.3.1 and stratified by subsequent treatment following alectinib.

Phase 2 objectives will be assessed in a sample of patients who received alectinib as front-line therapy and stratified by subsequent treatment following alectinib.

The number of cohort stratifications may depend on sample size of patients receiving subsequent therapy following alectinib¹ including chemotherapy (further stratified into platinum doublet and single agent), immunotherapy, and ALK inhibitors. Up to 5 cohorts will be considered:

Cohort A: Patients who received alectinib during the study period (overall population)

Cohort B (alectinib only cohort): Patients with ongoing alectinib treatment, or patients who discontinued alectinib, and patients who did not have a subsequent treatment²

Cohort C: patients who received alectinib followed by treatment X (top 3 most frequent)

Cohort D: patients who received alectinib followed by treatment Y (top 3 most frequent)

Cohort E: patients who received alectinib followed by treatment Z (top 3 most frequent)

¹ Final cohorts will be decided upon sample size. Patients receiving chemotherapy and immunotherapy after initiating alectinib will be included in the patient sample. Chemotherapy cohort may be further stratified into platinum doublet chemotherapy and single agent chemotherapy depending on sample size.

[figure not shown]
² Patients with ongoing alectinib treatment, patients who discontinued alectinib and patients who did not have a subsequent treatment may be analyzed as separate cohorts depending on sample size of patients

9.2. Study Design Phase 3 (study refresh and exploratory analysis)

During the Phase 3 data refresh, patients who have evidence of receiving alectinib during 01 June 2017 and 31 August 2020 will be eligible for inclusion in the study. Patients will be followed longitudinally until 31 August 2021, last patient record or date of death, whichever occurs first.

An overview of the study design for Phase 3 is presented in Figure 2.

Figure 2. Phase 3 data refresh study design

^{*}Last visit = last physical encounter, X = Additional visit or record of death

Phase 3 structured data objectives will be assessed among patients who meet study eligibility criteria as specified in 9.3.1 and stratified by subsequent treatment following alectinib.

Cohort A: All alectinib treated patients (overall population)

Cohort B (Alectinib only cohort): Alectinib treatment ongoing, or discontinued and no subsequent treatment³

Cohort C: Alectinib followed by treatment X (top 3 most frequent)

Cohort D: Alectinib followed by treatment Y (top 3 most frequent)

Cohort E: Alectinib followed by treatment Z (top 3 most frequent)

[figure not shown]
³ Patients with ongoing alectibin treatment, patients who discontinued alectinib and patients who did not have a subsequent treatment may be analyzed as separate cohorts depending on sample size of patients

Two groups of patients are planned for chart review during Phase 3. The first group includes patients from Phase 2 chart review who had ongoing treatment at the end of the observation period (31 December 2019). These patients will undergo additional follow-up through 31 August 2021.

An additional sample of approximately 100 patients who meet the Phase 3 eligibility criteria and received alectinib as front-line therapy and received subsequent treatment among the following groups will also undergo chart review:

- Alectinib → lorlatinib
- Alectinib → crizotinib
- Alectinib → brigatinib
- Alectinib only
- Alectinib → chemotherapy (optional)

Figure 3. Phase 3 exploratory analysis study design

^{*}Last visit = last physical encounter, X = Additional visit or record of death

9.3. Setting

The study population will consist of patients with a diagnosis of NSCLC receiving alectinib within The US Oncology Network and Non-Network sites. The US Oncology Network includes approximately 1,400 affiliated physicians operating in over 480 sites of care across states and treats approximately 1.2 million US cancer patients annually. There are more than 2,650 active Non-Network supported oncology and non-oncology sites of care. [19]

Figure 1 and Figure 2 presents graphical depictions of the study time periods, which are as follows:

- Phase 1 and 2 study observation period: 01 June 2017 31 December 2019.
- Phase 1 and 2 study identification period: 01 June 2017 30 June 2019.
- Phase 3 study refresh observation period: 01 June 2017 31 August 2021.
- Phase 3 study refresh identification period: 01 June 2017 31 August 2020.
- Phase 3 exploratory analysis study observation period: 02 November 2018 31 August 2021.
- Phase 3 exploratory analysis study identification period: 02 November 2018 31 August 2020.
- Phase 1 and 2 index date-1: start date of alectinib treatment during the study identification period
- Phase 1 and 2 index date-2: start date of the subsequent treatment following alectinib, among patients who receive the next treatment during the study observation period
- Phase 3 study refresh index date-1: start date of alectinib treatment during the study identification period
- Phase 3 study refresh index date-2: start date of the subsequent treatment following alectinib, among patients who receive the next treatment during the study observation period
- Phase 3 exploratory analysis index date-1: start date of lorlatinib treatment during the study identification period
- Phase 3 exploratory analysis index date-2: start date of lorlatinib treatment among patients who receive next treatment during the study observation period
- Baseline: The baseline period or "at index" includes up to 30 days prior to and up to 30 days after index. If a patient has multiple baseline values for a particular demographic or clinical characteristic during this ± 30-day time frame, the one closest (in absolute value) prior to the index date will be used. If no values prior to index are available, then the one closest to the index date up to 30 days after will be used.
- Prior medical history: Patients' available history in the iKnowMed (iKM) EHR will vary based on the length of disease and the time within The US Oncology Network. Disease characteristics such as time of NSCLC diagnosis and date of metastatic

disease will take into account patients' available medical history. The prior medical history period will end the day prior to the index date-1.

• Follow-up: Patients will be followed through the end of the study observation period, date of last visit or date of death, whichever occurs first. For analysis, patients will have a potential of at least 6 months of follow-up duration; however, patients will have variable follow-up time periods, depending on their index dates and last contact dates.

9.3.1. Phase 1 and 2 (original study) and Phase 3 (refresh study) population Inclusion criteria

Patients must meet all of the following inclusion criteria to be eligible for inclusion in the study:

- 1. Patients with a documented diagnosis of NSCLC.
- 2. Patients \geq 18 years of age at initial recorded diagnosis of NSCLC.
- 3. Patients who received treatment with alectinib within The US Oncology Network or Non-Network sites during the study identification period.
- 4. During the study observation period, patients observed with at least 2 visits⁴ after the index date-1.

Exclusion criteria

Patients meeting any of the following criteria will not be included in the study:

- 1. Receipt of treatment indicated for another primary cancer or diagnosis of another primary cancer (with the exception of non-melanotic skin cancer), within 5 years of index date-1 will be excluded.
- 2. Patients enrolled in clinical trials prior to receiving alectinib during the study ID period (index date-1), will be excluded.

⁴ Visits are defined as physical encounters with the practice, detected by vital sign records. The second and third visits must be observed after the index date-1 to demonstrate continuity of care. There is no required time span between the additional visits and the index date-1.

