				Missouri, Nebraska, North Dakota and South Dakota Northeast: Connecticut, Maine, Massachusetts, New Hampshire, Rhode Island, Vermont, Pennsylvania, New Jersey and New York South: Delaware, Florida, Georgia, Maryland, North Carolina, South Carolina, Virginia, Washington D.C., West Virginia, Alabama, Kentucky, Mississippi, Tennessee, Arkansas, Louisiana, Oklahoma and Texas West: Arizona, Colorado, Idaho, Montana, Nevada, New Mexico, Utah, Wyoming, California, Oregon and Washington State Missing clinic values will be captured in a "no information" category. Some of the regions may need to be collapsed if there are small sample sizes (e.g., South vs. non- South). This determination will be confirmed after reviewing sample sizes and the added value to the study with Ontada's Privacy and Compliance team.
Disease charact				
Initial NSCLC diagnosis	iKM structured data + chart review	Eligibility criteria, Baseline characteristic	Medical history prior to index	To assess NSCLC diagnoses that occurred prior to index date-1, patients' available medical history in iKM will be searched. The completeness of this history will vary based on the length of disease and the time within The US Oncology Network or Non-Network. Records may also be incomplete for patients with an initial NSCLC diagnosis that occurred outside of The US Oncology Network or Non-Network. Diagnosis of NSCLC will be determined through a review of iKM's discrete diagnosis and histology fields, which are populated during the routine course of care (International Classification of Diseases [ICD] codes will not be used). If no initial diagnosis date is documented, the first recorded diagnosis date in iKM will be used. This date will be used in calculations, not reported separately. Patients without a recorded diagnosis of NSCLC will be excluded from the study.
Stage at initial NSCLC diagnosis	iKM structured data	Baseline characteristic	Medical history prior to index	Categorized as: Early stage (IA, IB, IIA, IIIB) Limited/Regional (IIIA) Locally advanced (IIIB)

Table 1. Study variables and operational definitions

Variable	Source(s)	Role(s) in study	Period of measurement	Operational definition
		•		Metastatic (IV) Unknown

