Date of metastatic disease diagnosis	iKM structured data + chart review	Baseline characteristic	Medical history prior to index	Date of first recorded diagnosis of metastatic disease within the EHR. Patients will be qualified initially based on the date identified in the structured data; this will be confirmed during chart review among patients selected for chart review. Ultimately, the primary source will be the chart if available. All patients receiving ALK inhibitors are assumed to be metastatic at time of ALK inhibitor treatment. Structured data will confirm the patient as metastatic and as available, indicate the earliest associated date of any of these criteria: 1) Stage IV disease 2) TNM with M value of 1 3) Record of location of metastatic disease 4) Current or prior disease status containing reference to metastatic disease
Metastatic disease at diagnosis	iKM structured data + chart review	Categorized as: Baseline characteristic	At diagnosis	Categorized as: Yes No No information Note, "no information" can indicate that metastases were not documented in the chart, not necessarily that patients did not have metastases.
Distant metastatic site(s) at index date-1 (alectinib or lorlatinib start date)	iKM structured data + chart review	Baseline characteristic	Baseline	Baseline metastatic location(s) will be identified and categorized as: Bone (single) Bone (multiple) Brain CNS Liver (single) Liver (multiple) Lung (single) Lung (single) Lung (pleural effusion) Lymph nodes (regional) Lymph nodes (distant) Ovary Other No information Note, "no information" can indicate that metastases were not documented in the chart, not necessarily that patients did not have metastases.

Table 1. Study variables and operational definitions

Variable	Source(s)	Role(s) in study	Period of measurement	Operational definition
Tumor histology	iKM structured data	Baseline characteristic	Baseline	Categorized as: Adenocarcinoma Squamous Large Not otherwise specified (NOS) Missing/unknown
ALK testing order source and date	iKM Chart Review	Baseline characteristic	Baseline	Categorized as: Lab report Order requisition Pathology report Progress note
ALK mutation status	iKM structured data + Chart Review	Baseline characteristic	Baseline	Categorized as: Not performed Positive fusion/rearrangement Negative Equivocal Indeterminate QNS Other Inconclusive Not documented If multiple test results are available, used last documented value

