9.6. Study size

A preliminary feasibility assessment for Phases 1 and 2 identified 293 patients who were treated with alectinib after 01 November 2017, with approximately half treated in the front-line setting. Of the 293 patients receiving alectinib, 74% (n=217) patients had an ALK result. Approximately 20-30% of the 293 patients received a subsequent therapy after alectinib. It is estimated that approximately 300 patients will be included in the Phase 2 structured data analysis. Targeted chart review for Phase 2 is proposed to occur on 150 patients receiving alectinib to identify at least 100 patients who received alectinib as front-line. In the event the total number of eligible patients following structured data screening exceeds the planned number of charts for review, a random sample will be selected.

For Phase 3 structured analysis, a preliminary feasibility assessment identified 521 patients who were treated with alectinib from 01 June 1 2017 through 31 December 2020. Chart review for Phase 3 will include patients who had ongoing treatment at the end of Phase 2

study period, and an additional 125 patients will be targeted to identify 100 new patient who received alectinib as front-line therapy. For Phase 3 exploratory analysis, a preliminary feasibility assessment identified 134 patients who were treated with lorlatinib from 01 November 2018 through 31 December 31 2020.

The final study population for analysis will be defined after identification and review of the patient population meeting the eligibility criteria in the iKM database. A specific power calculation will not be performed as this is a descriptive analysis.

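### Table 1's stage groups list IIIB twice and IIB nowhere, and the closest-value baseline rule does not exempt metastatic sites, several of which can co-exist

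*Combined protocol and SAP*

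**What the plan says.** **Stage.** In Table 1 (Section 9.4), the row for stage at initial NSCLC diagnosis groups patients as "Early stage (IA, IB, IIA, IIIB) Limited/Regional (IIIA) Locally advanced (IIIB"), followed by a metastatic group (IV) and an unknown group.

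**Baseline rule.** Section 9.3 defines baseline as 30 days either side of index. "If a patient has multiple baseline values for a particular demographic or clinical characteristic during this ± 30-day time frame", then "the one closest (in absolute value) prior to the index date will be used". A value after index is used only when there is none before it. No type of characteristic is exempted.

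**Metastatic sites.** The Table 1 row for distant metastatic sites at index date-1 has baseline as its period of measurement. It reads "Baseline metastatic location(s) will be identified and categorized as: Bone (single) Bone (multiple) Brain CNS Liver (single) Liver (multiple"), and continues through lung, lymph nodes, ovary and others. It does not say how entries from different dates are combined. Elsewhere the table does set a row-specific rule: for ALK status, "If multiple test results are available, used last documented value".

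**Use of these variables.** Describing clinical characteristics is Objective 1 (structured data), Objective 5 (chart review) and part of Objective 11 (lorlatinib). Section 9.8.3 applies chi-square or Fisher's exact tests, at the 0.05 level, to categorical variables compared between treatment groups or strata. Section 9.8 states that no separate analysis plan will be written.

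**The concern.** A grouping that is to be tabulated and tested must place every patient in exactly one category. The stage list does not, so whoever programs it must decide where IIB and IIIB go, and the protocol offers no authority for the choice.

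The closest-value rule suits a measure such as ECOG, where a newer value replaces an older one. Metastatic sites do not replace each other: a bone record does not cancel an earlier brain record. If the rule is applied to the site row, a patient with two sites entered on different days is shown with one, and the tables understate both the number of sites and the frequency of each.

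The clinical profile is itself a reported result here, and Sections 9.3 and 9.4 are the only specification the programmer will have. Two competent analysts could therefore produce different stage and site tables from the same data.

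**Working it through.** There is no stated figure to reproduce. Section 9.6 says "A specific power calculation will not be performed as this is a descriptive analysis", and no stage or site distribution is given. The check is logical.

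**Step 1: map each stage to the categories as written (Table 1).**

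| Stage | Categories as written | Count | Count if the early list ended in IIB |
|---|---|---|---|
| IA | Early | 1 | 1 |
| IB | Early | 1 | 1 |
| IIA | Early | 1 | 1 |
| IIB | none | 0 | 1 |
| IIIA | Limited/Regional | 1 | 1 |
| IIIB | Early; Locally advanced | 2 | 1 |
| IV | Metastatic | 1 | 1 |

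Five of the seven stages map to one group, one maps to two and one to none. Replacing IIIB by IIB in the early list, which is an assumption about what was meant, gives one group for all seven.

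**Step 2: apply the baseline rule to invented site records.** Days are relative to index, and the patients are illustrations only. Three readings are compared: (A) one value is kept; (B) the whole set of sites entered on the closest date is kept; (C) each site is its own characteristic, so every site in the window is kept.

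| Records | A: one value | B: set on closest date | C: each site separately |
|---|---|---|---|
| Brain day -25, bone day -5 | bone | bone | brain, bone |
| Brain day -5, liver day -5 | tie, no rule given | brain, liver | brain, liver |
| Bone day -10, brain day +3 | bone | bone | bone, brain |
| Brain day -200, bone day -5 | bone | bone | bone |

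- Rows 1 and 3: A and B lose a site that C keeps. In row 3 the loss occurs because values after index count only if nothing precedes index.
- Row 2: A gives no answer, because no tie-break is stated.
- Row 4: no reading recovers the brain record, which lies outside the window. By contrast, the neighbouring row for the date of metastatic diagnosis uses medical history before index and accepts a record of metastatic location as evidence. An old site record can therefore date the metastatic disease and yet be absent from the site table.

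**Step 3: trace where the variables are used.** Neither stage group nor metastatic site appears in the eligibility criteria (Sections 9.3.1 and 9.3.2) or in the definitions of OS, PFS and DOT (Table 1 and Section 9.8.3).

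**The case against.** The strongest reply has four parts.

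1. *The stage list is a typing slip.* The early list runs IA, IB, IIA and then an entry one character away from IIB, and IIIB has its own group. An analyst would notice the overlap when coding, and Sections 9.7, 9.8.2 and 9.9 plan checks of values and logic. This stands as an account of the cause, and a PDF-reading error cannot be excluded either. It does not correct the text: if the source reads the same, no other section repairs it. A reader might infer that IIB patients will be reported as unknown and IIIB patients counted twice. The documents say neither; they leave both cases unresolved.

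2. *The site row already implies that all sites are kept.* Its title and definition use the plural, and some categories denote multiple lesions. This stands in part. Reading C is available, so one cannot conclude that the plan orders a single site per patient. But the general rule has no exception and the row has no override, although the ALK status row shows that overrides were written where wanted. Reading B is equally available and still loses sites.

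3. *Bias between strata is not shown.* A reader might infer greater loss among non-front-line and lorlatinib patients because their metastases were recorded earlier. That requires sites to be dated once and not re-entered near index, and the documents do not say how the EHR stores them. Chart data supersede structured data where available (Section 9.8.1), and the lorlatinib analysis is descriptive with no stated test against alectinib strata (Section 9.8.3). This objection stands.

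4. *Using all prior history would bring a bias of its own.* Section 9.3 says available history varies with disease length and time in the network, so longer records would accumulate more sites, and a variable defined at index would become one defined as ever recorded. This also stands and limits the fix.

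**Conclusion.** The concern holds in two parts of different strength.

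- **Stage:** the definition is wrong as written. The groups are neither mutually exclusive (IIIB has two) nor exhaustive (IIB has none). The only reservation is that the source PDF should be checked.
- **Sites:** the general baseline rule conflicts with a row that can hold several values. Applied without an exception, the rule drops sites recorded on other dates in the window. On the kinder per-site reading nothing inside the window is lost, so the defect is an unresolved rule rather than certain misclassification.

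The effect is limited to the clinical-profile tables and the tests on them. Its size is unknown: neither the number of patients affected nor any difference between strata can be determined from the documents. A reader might turn the invented patients into a proportion of sites lost, but that proportion would only reflect how many sites the example was given.

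**What to change.** 1. **Stage row, Table 1.** After checking the source PDF, list IIB in the early-stage group and IIIB only under locally advanced. Cost: one correction.
2. **Baseline rule, Section 9.3, and the site row, Table 1.** Exempt metastatic sites from the closest-value rule. Report every site recorded within the existing window of 30 days either side of index as its own non-exclusive yes/no indicator. Keep the closest-value rule for single-valued measures such as ECOG. Cost: a sentence in each place and a small programming change. Percentages across sites may then sum to more than 100, which a table footnote should say.
3. **Optional.** For sites recorded only before day -30, add a separate summary labelled as ever recorded up to index. It should supplement the at-index variable, not replace it. Its downsides should be stated beside it: resolved sites are counted, and patients with longer records accumulate more sites.
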